### 3. ANALYSIS POPULATIONS

In accordance with guidance from the International Conference of Harmonization of Technical Requirements for Registration of Pharmaceuticals for Human Use (ICH) guideline [ICH E9](#) Statistical Principles for Clinical Trials (1998), the following populations of analysis will be used for all statistical analyses.

#### 3.1. Efficacy Analysis Sets

The full analysis set (FAS) includes all randomized patients. Efficacy analyses will be based on the treatment allocated at randomization (as randomized).

The per-protocol set (PPS) includes all patients in the FAS except for those who are excluded because of major efficacy-related protocol violations. A major efficacy-related protocol violation is one that may affect the interpretation of study results. The criteria of major efficacy-related protocol deviation are defined as following:

- Patients who were randomized more than once
  - Any major violations of efficacy-related entry criteria
    - Inclusion criteria 3, 4, 5, 6, 7, 8 and 9\*
    - Exclusion criteria 1, 2\*, 3\*, 4, 5, 6\*, 8, 9, 10,11, 19
  - Patients who received <80% of the scheduled doses during the study treatment period
- \*Note: Will be adjudicated on a case by case basis in blinded fashion prior to database lock

Final determination of the PPS will be made in a blinded manner prior to the database lock.

All efficacy variables will be evaluated on the FAS; the primary endpoint and key secondary endpoints will also be evaluated on the PPS. Analysis on the FAS will be considered to be primary.

#### 3.2. The Safety Analysis Set (SAF)

The safety analysis set (SAF) includes all randomized patients who receive at least one injection of study drug, and will be analyzed as treated. Treatment compliance/administration and all clinical safety variables will be summarized based on the SAF.

The actual treatment group as treated is defined by the following rules:

- For a patient randomized to dupilumab (Q2W or Q4W), if the patient received all placebo injections, the actual treatment will be assigned as placebo.
- For a patient randomized to dupilumab (Q2W or Q4W), if the patient received at least one dupilumab injection, the actual treatment will be same as the planned treatment.
- For patients randomized to placebo but accidentally received dupilumab injections, the actual treatment will be assigned as dupilumab 300 mg Q4W.

In addition:

- Nonrandomized but treated patients will not be part of the safety population; however, their safety data will be presented separately.
- Randomized patients for whom it is unclear whether they took the study drug will be included in the safety population as randomized.

For safety summaries, three analysis periods are defined as follows:

- Week 16 treatment period is defined as:
  - Day 1 to the study completion date of the planned Week 16 visit (or study day 113 starting from the first dose of study drug if the date of the Week 16 treatment visit is unavailable) for those patients who completed the 16 week treatment period
  - Day 1 to the date of early termination visit, for those patients who did not complete the 16 week treatment period
- Follow-up period is defined as:
  - The date after the week 16 visit date (or study day 113 starting from the first dose of study drug if the date of Week 16 treatment visit is unavailable) to the date of the end of study visit
- Overall study Period is defined as:
  - Day 1 to the date of the end of study visit

The SAF will be the basis for the analyses for the treatment period and overall study period; however, for the analyses for the follow-up period, only a subset of SAF will be included, which is defined as the patients who entered the follow-up period and had at least one visit after week 16 treatment visit.

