### 5.4.2. Study Drug Discontinuation

Patients who permanently discontinue from study drug and who do not withdraw from the study will be asked to return to the clinic for all remaining study visits per the visit schedule.

Patients who opt to withdraw from the study will be asked to complete study assessments, per section 6.1.

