- Placebo treatment group: Patients will receive placebo matching dupilumab Q2W (including doubling the amount of placebo on day 1 to match the loading dose). In order to maintain blinding for the study, patients in the <60 kg weight stratum will receive, in a 1:1 ratio, either placebo matching 200 mg dupilumab (including doubling the amount of placebo on day 1 to match the loading dose) or placebo matching 300 mg dupilumab (including doubling the amount of placebo on day 1 to match the loading dose). In the ≥60 kg weight stratum, the patients randomized to the placebo group will receive placebo matching 300 mg dupilumab (including doubling the amount of placebo on day 1 to match the loading dose).

In order to maintain blinding, all patients will receive an injection Q2W from day 1 to week 14. Patients will receive placebo injection at the weeks dupilumab is not given.

During the treatment period, patients will have weekly in-clinic visits through week 4, and then in-clinic visits every 4 weeks through week 16 with weekly telephone visits in between the in-clinic visits. Patients and/or parents/caregivers (as deemed appropriate based on age of patient) will be trained on injecting study drug during in-clinic visit 2 (day 1) to visit 6 (week 4). During weeks in which no in-clinic visit is scheduled, patients will either self-inject study drug or the parent/caregiver will administer study drug to the patient. In case patients do not want to self-inject and the parent/caregiver do not want to administer study drug to patient, patients may have the clinic staff administer all the study drug injections in the clinic. Safety, laboratory, and clinical assessments will be performed at specified clinic visits, as noted in schedule of event [Appendix 10.2](#). The end of treatment period visit will occur at week 16, two weeks after the last dose of study drug. The co-primary endpoints will be assessed at this visit. If patients prematurely discontinue study treatment, the patients will be encouraged to stay in the study to have data collected at all remaining scheduled visits until completion of the planned end of study visit.

Patients who participate in the study may subsequently be eligible to participate in an open-label extension study.

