- Treatment-emergent AEs (TEAEs) are AEs that developed or worsened in severity compared to the baseline during the treatment and follow-up period. As only the worsening pre-existing AEs and new AEs reported during the treatment and follow-up period will be collected in the study, all AEs collected during the treatment and follow-up period are considered as TEAEs.
- TEAEs during the 16 week treatment period are AEs with onset after the first dose up to the week 16 visit date (study day 113 if the week 16 visit date is missing), or early termination visit whichever is earlier. TEAEs that have an onset during the 16 week treatment period and continued afterwards into follow-up period will be counted only once as TEAEs during the 16 week treatment period.
- TEAEs during the Follow-up period are AEs with onset after the week 16 visit date up to the end of study.

Adverse event of special interest (AESI) category:

- Anaphylactic reactions
- Systemic or severe hypersensitivity reactions
- Malignancy (except in situ carcinoma of the cervix, non-metastatic squamous or basal cell carcinoma of the skin)
- Helminthic infections
- Suicide-related events
- Any type of conjunctivitis or blepharitis (severe or serious)
- Keratitis (any event regardless of severity or seriousness)

[Appendix 10.54](#) provides a list of AESIs search criteria.

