#### Analysis of incidence of TEAE-related variables

- Incidence of skin infection TEAE (excluding herpetic infections) from baseline through week 16
- Incidence of treatment-emergent serious adverse events from baseline through week 16

These endpoints will be analyzed for patient in SAF. The week 16 treatment period is defined in Section 3.2. The Cochran-Mantel-Haenszel test adjusted for randomization strata will be used for the percentage of patients with events described above through week 16.

Multiplicity Considerations

The following multiplicity adjustment approach, a hierarchical procedure, will be used to control the overall Type-I error rate at 0.05 for the primary endpoint and the secondary endpoints across the 2 dupilumab dose regimens versus placebo. Each hypothesis will be formally tested only if the preceding one is significant at the 2-sided 0.05 significance level. The hierarchical testing order is shown in below table (all comparisons are with the placebo).

	Endpoints	Dupilumab	
		Q4W group	Q2W group
Primary endpoint	Proportion of patients with IGA 0 to 1 (on a 5-point scale) at week 16	10	1
Co-primary endpoint for ex-US countries, key secondary for US	Proportion of patients with EASI-75 ( $\geq 75\%$ improvement from baseline) at week 16	9	2
Key Secondary endpoints	Percent change in EASI score from baseline to week 16	11	3
	Percent change from baseline to week 16 in weekly average of daily peak Pruritus NRS	12	4
	Proportion of patients with improvement (reduction) of weekly average of daily peak Pruritus NRS $\geq 3$ from baseline to week 16	13	5
	Proportion of patients with improvement (reduction) of weekly average of daily peak Pruritus NRS $\geq 4$ from baseline to week 16	14	6
Secondary endpoints	Proportion of patients with EASI-50 at week 16	15	7
	Proportion of patients with EASI-90 at week 16	16	8
	Time to onset of effect on pruritus during the 16-week treatment period ( $\geq 3$ point reduction of weekly average of peak Pruritus NRS from baseline)	25	17
	Time to onset of effect on pruritus during the 16-week treatment period ( $\geq 4$ point reduction of weekly average of peak Pruritus NRS from baseline)	26	18
	Change from baseline to week 16 in percent BSA affected by AD	27	19
	Percent change from baseline to week 16 in SCORAD	28	20
	Change from baseline to week 16 in CDLQI	29	21
	Change from baseline to week 16 in POEM	30	22

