	Change from baseline to week 16 in weekly average of daily peak Pruritus NRS	31	23
	Percent change from baseline to week 4 in weekly average of daily peak Pruritus	32	24
	Change from baseline to week 16 in HADS	35	33
	Proportion of patients with improvement (reduction) of weekly average of daily peak Pruritus NRS $\geq 4$ from baseline to week 4	36	34
	Incidence of skin-infection TEAEs (excluding herpetic infections) through week 16	39	37
	Incidence of serious TEAEs through week 16	40	38

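### SAP 3.2 and SAP 4.5.1 end the week 16 treatment period on different dates for patients who did not complete it

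*SAP*

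**What the plan says.** SAP 3.2 sets the week 16 treatment period with two bullets. Patients who completed it are counted until they attend at week 16, with this fallback: "or study day 113 starting from the first dose of study drug if the date of the Week 16 treatment visit is unavailable". Non-completers have a different rule: "Day 1 to the date of early termination visit, for those patients who did not complete the 16 week treatment period". The follow-up period in the same section starts after the week 16 visit date or day 113, with no separate rule for non-completers.

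SAP 4.5.1 defines TEAEs in the 16-week period with one rule for everyone. The window closes at the week 16 visit date ("study day 113 if the week 16 visit date is missing), or early termination visit whichever is earlier").

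SAP 5.7.2 says which definition the tested endpoints use: "The week 16 treatment period is defined in Section 3.2". The endpoints are "Incidence of skin-infection TEAEs (excluding herpetic infections) through week 16" (rank 37 for Q2W, 39 for Q4W) and "Incidence of serious TEAEs through week 16" (rank 38 for Q2W, 40 for Q4W).

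Patients who stop study drug but do not withdraw "will be asked to return to the clinic for all remaining study visits per the visit schedule" (Protocol 5.4.2). SAP 2.3 encourages them to stay "until completion of the planned end of study visit", which is week 28, day 197.

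**The concern.** One named period has two end-date rules, and the tested endpoints are sent to the rule without a cap. A non-completer whose early termination visit falls after day 113 is counted up to that visit under SAP 3.2, but only to day 113 under SAP 4.5.1. A non-completer with no early termination visit has no end date under SAP 3.2.

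The choice decides who has an event in ranks 37 to 40. It also affects the week-16 TEAE tables, for which SAP 5.8.1 does not say which section governs, and the safety Cox models in SAP 5.8.1, which censor at the end of the treatment period. A programmer would have to choose between the two sections, and pre-specification is meant to remove that choice. Because only non-completers are affected, arms that differ in non-completion could have the extra follow-up to different degrees.

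**Working it through.** **Calendar.** Study day of week w = 7w + 1. Week 16: 7 × 16 + 1 = 113, which reproduces the SAP's day 113. Week 28: 7 × 28 + 1 = 197, which matches the schedule of events.

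**Rules compared** (ET = early termination visit)
- SAP 3.2: week 16 visit date (or 113) for a completer; otherwise the ET date.
- SAP 4.5.1: the earlier of the week 16 visit date (or 113) and the ET date.

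| Patient pattern | SAP 3.2 end day | SAP 4.5.1 end day |
|---|---|---|
| Completer, week 16 visit on day 113 | 113 | 113 |
| Completer, week 16 visit on day 116 | 116 | 116 |
| Non-completer, ET on day 60 | 60 | 60 |
| Non-completer, no week 16 visit, ET on day 127 | 127 | 113 |
| Non-completer, no ET visit | none | 113 |
| Drug stopped, week 16 visit on day 113, ET on day 150, if classed as non-completer | 150 | 113 |
| Same, ET on day 196 | 196 | 113 |

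The rules agree for completers and for ET before day 113. They part only for late or absent ET visits. Day 116 appears in both columns because the visit window is ±3 days, so day 113 is not a strict limit under either section.

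**Which patients count as non-completers.** The SAP does not define the term. The documents' usage points to attendance at week 16:
- Protocol 3.2 describes completion of the period as the week 16 visit, or earlier for patients withdrawn from the study.
- Protocol 5.8 equates premature discontinuation with not completing the end-of-treatment visit.
- Protocol 9.5.2.1 and SAP 5.7.1 separate staying to the end of the treatment period from being on drug.

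On that usage the last two rows of the table describe completers, whose period ends on day 113 under both rules. The rows with ET on day 127 and with no ET visit remain.

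**Size for one affected patient.** The documents give no event rates, so this is an illustration with an assumed constant hazard. If r is the risk by day 113, the risk by day d is 1 − (1 − r)^(d/113).

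| Assumed r | d = 127 | d = 150 | d = 196 |
|---|---|---|---|
| 5% | 5.6% | 6.6% | 8.5% |
| 10% | 11.2% | 13.1% | 16.7% |
| 20% | 22.2% | 25.6% | 32.1% |

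Day 127 is the last day that SAP 6.4 maps an ET visit to week 16, so the SAP itself allows for ET visits between days 114 and 127. For an arm, multiply the rise by the share affected. With assumed shares of 2% and 10% and ET on day 127, the rise runs from 2% × 1.2 = 0.02 points (r = 10%) to 10% × 2.2 = 0.22 points (r = 20%).

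**The case against.** The strongest reply is that very few patients are affected. A patient who stops drug but attends week 16 is a completer in the documents' usual sense. A patient who stays in the study but has no week 16 visit date can be read as covered by the day-113 fallback in SAP 3.2. The passage in SAP 2.3 that places ET visits at or after week 16 concerns patients who must already have completed the week 16 visit. Patients who complete week 16 are offered the extension, which further limits late ET visits. All of this stands. It narrows the group without removing the conflict.

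Two further points stand in part. The SAP 3.2 follow-up period can overlap the uncapped treatment period: with ET on day 150, an event on day 140 falls inside both date ranges. But follow-up analyses are limited to patients who entered follow-up and had a visit after the week 16 visit, so double counting is not automatic. Unequal observation time is also not peculiar to this defect, because under SAP 4.5.1 patients who terminate early are still observed for less time than completers.

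A reader might infer that anyone who stops drug and leaves during follow-up is counted almost to week 28, giving 28/16 = 1.75, or 75% more time at risk. With incidence r by week 16 and affected share k, that reading gives k × [(1 − (1 − r)^1.75) − r]: 0.14 points for k = 2%, r = 10%, and 1.23 points for k = 10%, r = 20%. The documents do not support using these as estimates. They need non-completion to mean stopping drug, against the usage above, and they place every affected ET visit at week 28, where a patient would have an end of study visit instead. They are ceilings on assumed inputs.

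**Conclusion.** The inconsistency is real and holds under either meaning of completion. As written, the plan can count events after the week 16 time point in ranks 37 to 40, and it gives no end date for a non-completer without an early termination visit.

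On the documents' usual meaning, it reaches only patients with no week 16 visit and either a late early termination visit or none. It would extend to patients who stopped drug and left during follow-up only if the undefined term means stopping drug.

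The effect is small and cannot be quantified from the documents; every percentage shown rests on an assumed risk, hazard shape and affected share. The primary and key secondary tests are not touched, and ranks 37 to 40 are formally tested only if every earlier test succeeds. This is a minor correction, worth making because it removes a programming choice at almost no cost.

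**What to change.** In SAP 3.2:
- Define completing the 16-week treatment period as having reached the week 16 visit, whatever the study drug status.
- End the period for every patient at the earliest of (i) the week 16 visit date, or study day 113 if it is missing, and (ii) the early termination visit date.

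Use this single end date for ranks 37 to 40 and for the week-16 TEAE tables.

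For censoring in the SAP 5.8.1 Cox models, use the same date but no later than the last contact date. Without that limit, a patient lost on day 40 with no early termination visit would be credited with 113 − 40 = 73 unobserved event-free days.

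The cost is a few lines of SAP text, taken mainly from the rule already in SAP 4.5.1. No new data or protocol amendment is needed, and SAP 1 allows revision on blinded review before the final database lock.

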### **3.3. The Pharmacokinetic Analysis Set (PKAS)**

The PK analysis set includes all randomized patients who received any study drug and who had at least one non-missing drug concentration result following the first dose of study drug. Patients will be analyzed according to the treatment actually received.

### **3.4. The ADA Analysis Set (AAS)**

The ADA analysis set will consist of all patients who received any study drug and who had at least one non-missing ADA result after first dose of the study drug. Patients will be analyzed according to the treatment actually received.

The neutralizing antibody (NAb) Analysis Set (NAS) will consist of all patients who received any study drug and who had at least one non-missing Nab result or who had all samples negative in the ADA assay after first dose of the study drug. Patients will be analyzed according to the treatment actually received.

## 4. ANALYSIS VARIABLES

### 4.1. Demographic and Baseline Characteristics

The following demographic and baseline characteristics variables will be summarized:

- Demographic variables: Age at screening (year), age group ( $\geq 15$  to  $< 18$ ,  $\geq 12$  to  $< 15$ ), sex, ethnicity, race, baseline weight (kg) with grouping ( $< 60$  kg,  $\geq 60$  kg), height (m), BMI ( $\text{kg}/\text{m}^2$ ) with grouping ( $< 20$ ,  $\geq 20$ )
- Baseline characteristics: Duration of AD disease with grouping ( $< 13$  years,  $\geq 13$  years), Peak Pruritus numerical rating scale (NRS), Pruritus Categorical Scale (PCS), Investigator's Global Assessment (IGA) score, Eczema Area and Severity Index (EASI) score, SCORing Atopic Dermatitis (SCORAD) score, Body Surface Area (BSA) affected by Atopic Dermatitis, Patient global assessment of disease status, Patient Oriented Eczema Measure (POEM), Children's Dermatology Life Quality Index (CDLQI), Global Individual Signs score (GISS), Hospital Anxiety and Depression Scale (HADS) total score, HADS-Anxiety subscale score, HADS-Depression subscale score, Asthma Control Questionnaire (ACQ-5), and Total Nasal Symptom Score (TNSS), Patients with inadequate response to topicals (Yes/No) with the reasons for patients who are "No" for inadequate response to topicals

### 4.2. Medical History and Atopic Disease Medical History

Medical history will be coded to a Preferred Term (PT), High Level Term (HLT) and associated primary System Organ Class (SOC) according to the latest available version of MedDRA at the coding CRO. Information on conditions related to AD includes diagnosis of AD and AD treatment history, asthma, allergic conjunctivitis, allergic rhinitis, chronic rhinosinusitis, nasal polyps, eosinophilic esophagitis, food allergy, hives and other allergies due to medications, animals, plants, mold, dust mites, etc. Recent AD topical treatments history within 6 months before the screening visit is also collected. History of treatment with systemic immunosuppressants for AD (Cyclosporine, Systemic corticosteroids, Methotrexate, Azathiophrine and other treatments) during the last 6 months will also be collected.

### 4.3. Pre-treatment/Concomitant Medications and Procedures

Medications/Procedures will be recorded from the day of informed consent until the EOS visit. Medications will be coded to the ATC level 2 (therapeutic main group) and ATC level 4 (chemical/therapeutic subgroup), according to the latest available version of WHO Drug Dictionary (WHODD) at the coding CRO. Patients will be counted once in all ATC categories linked to the medication.

Procedures will be coded to a Preferred Term (PT), High Level Term (HLT) and associated primary System Organ Class (SOC) according to the latest available version of MedDRA at the coding CRO.

Pre-treatment medications/procedures: medications taken or procedures performed prior to administration of the first study drug.

Concomitant medications/procedures: medications taken or procedures performed following the first dose of study drug through the EOS visit.

- Concomitant medications/procedures during the 16 week treatment period are medications/procedures taken after the first dose up to the week 16 visit date or date of study day 113 if week 16 visit date is missing. Medications/procedures taken during the 16 week treatment period and continued afterwards into follow-up period will be counted only once as concomitant medications/procedures during the 16 week treatment period.
- Concomitant medications/procedures during the Follow-up period are medications/procedures taken after the week 16 visit date to end of study.

Prohibited concomitant medications/procedures: Treatment with the following concomitant medications is prohibited during the study:

- Treatment with a live (attenuated) vaccine
- Treatment with immunomodulating biologics
- Treatment with an investigational drug (other than dupilumab)
- Treatment with systemic nonsteroid immunosuppressant (may be used as rescue)
- Treatment with systemic corticosteroids (may be used as rescue)
- Treatment with TCS or TCI (may be used as rescue)
- Treatment with crisaborole (may be used as rescue)
- Initiation of treatment of AD with prescription moisturizers

The following concomitant procedures are prohibited during study participation:

- Major elective surgical procedures
- Tanning in a bed/booth
- Phototherapy (UVA, UVB, nbUVB, high dose UVA and PUVA) Rescue treatments

(i.e., both medications and procedures): If medically necessary (i.e., to control intolerable AD symptoms), rescue treatment for AD may be provided to study patients at the discretion of the investigator. For the purpose of efficacy analysis, patients who receive rescue treatment during the study will be considered treatment failures. If possible, investigators are encouraged to consider rescue initially with topical treatment (eg, medium/high potency TCS) and to escalate to systemic medications only for patients who do not respond adequately after at least 7 days of topical treatment. Topical calcineurin inhibitors may be used for rescue, alone or in combination with TCS, but the use of TCIs should be reserved for problem areas only (eg, face, neck, intertriginous and genital areas, etc.). Patients who receive systemic corticosteroids or systemic non-steroidal immunosuppressive drugs (eg, cyclosporine, methotrexate, mycophenolate-mofetil, azathioprine, etc.) as rescue treatment during the study will be discontinued permanently from the study drug. All patients will be asked to complete the scheduled study visits and assessments whether or not they complete study treatment and whether or not they receive rescue treatment for AD. Investigators should make every attempt to

conduct efficacy and safety assessments (eg, disease severity scores, safety laboratory tests) immediately before administering any rescue treatment. An unscheduled visit may be used for this purpose, if necessary.

Blinded adjudication of rescue treatments will be implemented before database locks by considering the type of medication or procedure, indication, timing, frequency and the potential impact of the use of the prohibited medication or procedure. The rescue treatments will be adjudicated by the clinical study director and the adjudication procedure will be documented.

